### **9.4.3. PK/PD Analyses**

For PK endpoints, analyses will be performed using the PK Analysis Set. Individual plasma total Mo and PUF Mo (as surrogate measures of ALXN1840) concentration-time data will be listed and plotted. The following total Mo (ALXN1840) PK parameters will be derived for individual participants and summarized with descriptive statistics. Analyses of PUF Mo may also be conducted:

- Maximum observed concentration ( $C_{max}$ ), time to maximum concentration ( $t_{max}$ ), AUC from time 0 to the time of last measurable concentration ( $AUC_t$ ), AUC from time 0 to infinity ( $AUC_{\infty}$ ), apparent terminal-phase elimination rate constant ( $\lambda_z$ ),  $t_{1/2}$ , clearance bioavailability (CL/F), and apparent volume of distribution ( $V_d/F$ ).

For exploratory endpoints such as plasma total Cu, ceruloplasmin, ceruloplasmin-bound Cu, and toxic copper as measured by LBC and/or NCC, a concentration-time data will be listed and summarized with descriptive statistics and plotted. The same analyses will be conducted on the absolute and percent changes from baseline of these concentration-time data.

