3. LIST OF ABBREVIATIONS AND DEFINITIONS OF TERMS

The following abbreviations and acronyms are used in this statistical analysis plan (SAP).

Table 1: Abbreviations and Acronyms

| Abbreviation or acronym | Explanation |
|--------------------------|--|
| λ_z | apparent terminal-phase elimination rate constant |
| ADME | absorption, distribution, metabolism, and excretion |
| AE | adverse event |
| ALT | alanine aminotransferase |
| AR | accumulation ratio |
| AST | aspartate aminotransferase |
| ATC | Anatomical Therapeutic Chemical |
| AUC | area under the plasma concentration versus time curve |
| AUC _t | AUC from time 0 to the last quantifiable concentration |
| AUC _{tau} | AUC over the dosing interval |
| AUC _∞ | AUC from time 0 to infinity |
| AUEC | area under the effect versus time curve |
| AUEC _t | AUEC from the start of dose administration to the last observed quantifiable concentration |
| BLQ | below the limit of quantification |
| BMI | body mass index |
| CL/F | apparent total body clearance |
| CE _{max} | maximum observed effect after dosing |
| C _{max} | maximum observed concentration |
| C _p | ceruloplasmin |
| C _p C | ceruloplasmin-bound copper |
| CRF | case report form |
| CRU | clinical research unit |
| C _t | observed concentration at the end of the dosing interval |
| CTCAE | Common Terminology Criteria for Adverse Events |
| C _{trough} | trough (predose) concentration observed at the start of the dosing interval |
| Cu | copper |
| CV | coefficient of variation |
| ECG | electrocardiogram |
| EOS | End of Study |
| FA | Full Analysis |
| GM | geometric mean |
| ICH | International Conference on Harmonization |
| ICF | informed consent form |
| ICP-MS | inductively coupled plasma mass spectrometry |
| INR | International Normalized Ratio |
| I/O | input/output |
| LBC | labile bound copper |
| LLOQ | lower limit of quantification |
| MedDRA | Medical Dictionary for Regulatory Activities |
| Mo | molybdenum |
| NCC | non-ceruloplasmin-bound copper |
| NCC _{corrected} | non-ceruloplasmin-bound Cu concentration corrected for the amount of Cu bound to the Cu-tetrathiomolybdate-albumin tripartite complex formed after ALXN1840 administration |

Table 1: Abbreviations and acronyms (Continued)

| Abbreviation or acronym | Explanation |
|--------------------------------|--|
| NCI | National Cancer Institute |
| PD | pharmacodynamic(s) |
| PK | pharmacokinetic(s) |
| PP | Per Protocol |
| PT | Preferred Term |

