7.5.1. Pharmacokinetic Concentration Analyses

Plasma concentrations of total Mo and PUF Mo (as surrogate measures of ALXN1840 PK) and time data will be presented in a data listing by participant. Plasma concentration data will be summarized separately by analyte, day and time point using the following descriptive statistics: number of participants, arithmetic mean, SD, coefficient of variation (CV), geometric mean

(GM), GMCV, median, minimum, and maximum. When calculating the GM, values of 0 will be discarded. For summary statistic calculations, plasma concentrations values below the lower limit of quantification (LLOQ) will be set to the LLOQ.

Mean plasma concentration versus scheduled time profiles will be presented in figures on both linear and semilogarithmic scales. Individual plasma concentration versus actual time profiles will be presented similarly. The time to reach steady-state will be graphically assessed by plotting mean plasma trough (predose) concentration observed at the start of the dosing interval (C_{trough}) versus study day in both linear and semilogarithmic scales. Additionally, time to steady state will be evaluated using stepwise testing for linear trend.

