7.5.3. Pharmacokinetic Parameter Analyses

The following plasma PK parameters, as data permit, will be calculated for total Mo and PUF Mo on Day 1 and Day 15 using noncompartmental methods with Phoenix[®] WinNonlin[®] (Certara USA Inc., Princeton, New Jersey) Version 8.0 or higher, or SAS Version 9.4 or higher (SAS Institute Inc., Cary, North Carolina), as applicable. Calculations will be based on the actual sampling times relative to the actual reference ALXN1840 dosing times recorded during the study.

- Time delay between the time of dosing and time of appearance of Mo concentration (T_{lag}) in plasma (Day 1 and Day 15)
- Maximum observed concentration (C_{max}) (Day 1 and Day 15)
- Time to maximum concentration (T_{max}) (Day 1 and Day 15)
- Trough (predose) concentration observed at the start of the dosing interval (C_{trough})
- Time of last quantifiable concentration (T_{last}) (Day 1 and Day 15)

- Observed concentration at the end of the dosing interval (C_{τ} , where $\tau = 24$ h) (Day 1 and Day 15)
- Area under the plasma concentration versus time curve (AUC) from time 0 to the last quantifiable concentration (AUC_t) (Day 1 and Day 15)
- AUC from time 0 to infinity (AUC_{∞}) (Day 1 only)
- AUC over the dosing interval (AUC_{τ}) (Day 1 and Day 15)
- Apparent terminal-phase elimination rate constant (λ_z) (Day 1 and Day 15)
- Terminal elimination half-life ($t_{1/2}$) (Day 1 and Day 15)
- Apparent total body clearance (CL/F) (Day 1 and Day 15)
- Apparent volume of distribution (V_d/F) (Day 1 and Day 15)
- Accumulation ratio (AR) calculated as C_{\max} , C_{trough} , and AUC after repeat dosing on Day 15 divided by those after initial dosing on Day 1:
 - $C_{\max, \text{Day15}}/C_{\max, \text{Day1}}$
 - $C_{\text{trough}, \text{Day15}}/C_{\text{trough}, \text{Day1}}$
 - $AUC_{\tau, \text{Day15}}/AUC_{\tau, \text{Day1}}$

Additional plasma PK parameters may be calculated if deemed appropriate.

For the PK analysis, below the limit of quantification (BLQ) values prior to the first measurable concentration will be set to zero with the rest of all other BLQ values treated as missing

Pharmacokinetic parameters derived from plasma concentrations of total Mo and PUF Mo will be presented in data listings and summarized by analyte and day using the following descriptive statistics: number of participants, arithmetic mean, SD, arithmetic CV, GM, GMCV, median, minimum, and maximum.

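### SAP 7.5.3: as defined, the trough accumulation ratio divides the Day 15 value by a sample taken before any drug was given

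*SAP*

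**What the plan says.** SAP 7.5.3 introduces parameters that, "as data permit, will be calculated for total Mo and PUF Mo on Day 1 and Day 15". One of them is Ctrough: "Trough (predose) concentration observed at the start of the dosing interval". Unlike its neighbours in the list, it carries no day label. SAP Table 1 gives the same definition ("trough (predose) concentration observed at the start of the dosing interval"), and so does SAP 7.5.1, where time to steady state is "graphically assessed by plotting mean plasma trough (predose) concentration observed at the start of the dosing interval" against study day.

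A separate parameter, Ctau, is listed for Day 1 and Day 15: "Observed concentration at the end of the dosing interval", with the interval set at 24 hours.

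The accumulation ratio is then described as Cmax, Ctrough "and AUC after repeat dosing on Day 15 divided by those after initial dosing on Day 1". Three ratios are written out: Cmax, Ctrough and AUCtau, each Day 15 over Day 1. Ctau appears in none of them.

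For PK parameters, below-quantification "values prior to the first measurable concentration will be set to zero".

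**The concern.** The definition puts Ctrough Day 1 before the first dose, while the lead-in to the ratio puts it after. A programmer who follows the definition and one who follows the lead-in will use different samples and report different results under the same label.

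Under the definition, one of three accumulation ratios would compare drug plus background with background alone, for both total Mo and PUF Mo. It would be tabulated beside the Cmax and AUCtau ratios, where a reader would take all three as measures of the same thing. Plasma PK of total Mo and PUF Mo after repeated dosing is a secondary endpoint (SAP 5.2.2), so the table will be read.

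**Working it through.** The documents state no numerical accumulation ratio, so there is no figure to reproduce. The check is one of definitions, followed by an illustration of size.

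**Which sample is Ctrough Day 1?**

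- Protocol Table 2 (footnote b) has the pre-dose sample drawn within 1 hour before dosing.
- Exclusion criterion 22 (Protocol 5.2) bars anyone previously exposed to ALXN1840.
- Protocol 4.2 says that both total Mo and PUF Mo include dietary molybdate. The Day 1 pre-dose sample therefore holds only background Mo.
- SAP 9.2.4 defines Baseline as the last non-missing value on or before first dose, and SAP 7.1.3.2 lists total plasma Mo and PUF Mo as baseline characteristics. Where the Day 1 pre-dose sample is available, the literal ratio is Day 15 pre-dose over Baseline.
- The 24-hour sample after dose 1 is the Day 2 pre-dose sample (Protocol Table 2, Note 2; Figure 1 notes). In SAP terms that is Ctau Day 1. Nothing redefines Ctrough Day 1 as this sample, and SAP 9.3 adds no further method.

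**Size without a PK model, for either analyte**

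C(D15 pre)/C(D1 pre) = [C(D15 pre)/C(D2 pre)] × [C(D2 pre)/C(D1 pre)]

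The literal ratio is the Day 2-based ratio multiplied by C(Day 2 pre-dose)/C(Day 1 pre-dose).

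**Illustration for total Mo**

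Inputs: half-life about 51 h (Protocol 4.2, single dose) and dosing every 24 h. Assumptions: linear one-compartment kinetics and constant background. Let b be background Mo, c the drug-derived Mo 24 h after dose 1, and f = b/c. The documents do not give f, so a range is shown.

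- r = 2^(−24/51) = 0.7217
- Drug-derived Mo at Day 15 pre-dose (after 14 doses) = c(1 − r^14)/(1 − r) = 3.556c
- Drug-derived Mo at the Day 16 24-hour sample (after 15 doses) = c(1 − r^15)/(1 − r) = 3.566c
- Literal ratio = (b + 3.556c)/b = 1 + 3.556/f
- Day 15 pre-dose / Day 2 pre-dose = (f + 3.556)/(f + 1)
- Literal ratio as a multiple of the Day 2-based ratio = (1 + f)/f
- Ctau Day 15 / Ctau Day 1 = (f + 3.566)/(f + 1)

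| f (assumed) | Literal ratio | Day 15 pre / Day 2 pre | Multiple | Ctau ratio |
|---|---|---|---|---|
| 0.01 | 356.6 | 3.53 | 101 | 3.54 |
| 0.1 | 36.6 | 3.32 | 11 | 3.33 |
| 0.5 | 8.11 | 2.70 | 3 | 2.71 |
| 1 | 4.56 | 2.28 | 2 | 2.28 |
| 2 | 2.78 | 1.85 | 1.5 | 1.86 |

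Sensitivity to half-life at f = 0.1 (40 h and 60 h are assumed): at 40 h the literal ratio is 30.3, the Day 2-based ratio 2.75 and the Ctau ratio 2.76; at 60 h they are 41.4, 3.77 and 3.79.

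No half-life is given for PUF Mo, so no absolute values are offered for it.

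**Values below quantification**

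If the Day 1 pre-dose value is below quantification, the 7.5.3 rule makes the denominator zero and the ratio undefined. No LLOQ is given, so how often this would happen is unknown.

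**The case against.** The strongest reply is that one sample meets both descriptions. The Day 2 pre-dose sample is a pre-dose value at the start of an interval (the second one) and also follows the first dose, and the protocol itself labels it as the 24-hour sample of Day 1. Because Ctrough has no day label in the parameter list, this may well be what the authors meant.

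That is probably the intent, but it does not reconcile the text. It relabels the trough of the Day 2 interval as Day 1, which the subscript does not support. Applied consistently, it would also need a trough for an interval starting on Day 16, and there is none because dosing ends on Day 15. The 24-hour value already has its own name in the SAP, and the ratio does not use it.

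Other parts of the reply stand:

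- The size depends on an undocumented background level. The largest multiples come from the smallest assumed f.
- Parameters are calculated only as data permit, so a zero denominator gives a missing ratio rather than a misleading one.
- Concentrations are listed by participant and summarised by day and time point (SAP 7.5.1), so a wrong denominator could be detected.
- Changing only the denominator to the Day 2 pre-dose sample would cure the main fault, and its results barely differ from the Ctau ratio (3.32 against 3.33 at f = 0.1). The reason to prefer Ctau is that the Day 15 pre-dose sample precedes the Day 15 dose, whereas Ctau puts both terms after the dose they are named for.

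**Conclusion.** The concern holds. The definition of Ctrough and the lead-in to the ratio cannot both be followed, and the ratio as defined does not measure accumulation. This conclusion rests on the text alone. The multiplying factor C(Day 2 pre-dose)/C(Day 1 pre-dose) also needs no model. The absolute values for total Mo rest on the assumed background fractions, constant background, one-compartment kinetics and the approximate 51-hour half-life; over f = 0.01 to 2 the literal ratio is 101 to 1.5 times the Day 2-based one.

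The consequence is limited. Accumulation ratio is not among the parameters in Protocol 9.4.3 ("PK parameters will be derived for individual participants and summarized with descriptive statistics"), time to steady state is assessed separately by trough plots and trend testing (SAP 7.5.1), the Cmax and AUCtau ratios do not have this denominator problem, and the primary copper balance analysis is untouched. It is worth correcting because the error in that one ratio could be many-fold and the correction is simple.

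**What to change.** In SAP 7.5.3, replace Ctrough Day 15 / Ctrough Day 1 with Ctau Day 15 / Ctau Day 1 for both total Mo and PUF Mo, and name the samples: the 24-hour sample on Day 16 over the Day 2 pre-dose sample.

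This removes the pre-drug denominator but not the background Mo in both terms. Under the assumptions above, the ratio is 3.57 with no background, 3.33 at f = 0.1 and 2.71 at f = 0.5. Any background correction should be supportive and applied in the same way to all three ratios.

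The cost is one line in the SAP. Ctau is already defined for both days and both samples are already scheduled, so no new data or procedure is needed.

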7.5.4. Pharmacodynamic Parameter Analyses

The following plasma PD parameters, as data permit, will be calculated for total Cu, PUF Cu, and LBC on Day 1 and Day 15 using noncompartmental methods with Phoenix[®] WinNonlin[®] (Certara USA Inc., Princeton, New Jersey) Version 8.0 or higher, or SAS Version 9.4 or higher (SAS Institute Inc., Cary, North Carolina), as applicable. Calculations will be based on the actual sampling times relative to the actual reference ALXN1840 dosing times recorded during the study.

- Maximum observed effect after dosing (CE_{\max}) (Day 1 and Day 15)
- Time after dosing at which the maximum effect was observed (TE_{\max}) (Day 1 and Day 15)
- Time after dosing at which the last quantifiable concentration was observed (TE_{last}) (Day 1 and Day 15)
- Trough (predose) effect concentration observed at the start of the dosing interval (C_{trough})

- Area under the effect versus time curve (AUEC) from the start of dose administration to the last observed quantifiable concentration (AUEC_t) (Day 1 and Day 15)

Additional plasma PD parameters may be calculated if deemed appropriate.

For the PD parameter estimation, plasma concentrations below the LLOQ will be set to the LLOQ.

Pharmacodynamic parameters derived from plasma concentrations of total Cu, PUF Cu, and LBC will be presented in data listings and summarized by analyte and day using the following descriptive statistics: number of participants, arithmetic mean, SD, arithmetic CV, GM, GMCV, median, minimum, and maximum.

9. APPENDICES

9.1. Sample Size, Power, and Randomization

The study sample size is not based on null hypothesis significance testing. A sample size of 13 participants was selected based on convention for this type of study (Strickland, 1971). To accommodate a 25% dropout rate, approximately 17 participants will be enrolled and will receive study drug to achieve 13 evaluable participants who complete the study.

Randomization is not applicable. This is an open-label study in which all participants are expected to receive the same dose of ALXN1840.

9.2. Technical Specifications for Derived Variables

9.2.1. Adverse Events

The analysis of AEs is described in detail in Section 7.4.2.

Treatment-emergent AEs are events with start dates and start times on or after the date and time of the first study drug dose. If the start date of an AE is partially or completely missing and the end (stop) date and time of the AE does not indicate that it occurred prior to first dose, then the determination of treatment-emergent status will be based on the following:

- If the start year is after the year of the first study drug dose, then the AE is treatment-emergent; else,
- If the start year is the same as the year of the first study drug dose and
 - the start month is missing, then the AE is treatment-emergent; else if
 - the start month is present and is the same or after the month of the first study drug dose, then the AE is treatment-emergent; else,
- If the start date is completely missing, then the AE is treatment-emergent.

All other AEs are considered PTAEs (ie, AEs with partial or complete start dates before first study drug dose).

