5.3.1. Adverse Events

All AEs will be reported to the Investigator or qualified designee by the participant (or, when appropriate, by a caregiver, surrogate, or the participant's legally authorized representative).

All AEs and SAEs will be collected from the signing of the informed consent form (ICF) until the End of Study (EOS) Visit.

Each AE will be characterized (ie, verbatim term) and information regarding its seriousness, start and stop dates, toxicity, outcome, and causal relationship with the study drug will be provided. The safety evaluation will include an assessment of all AEs, SAEs, AE toxicity, and AE relatedness to study drug. Adverse event toxicity will be evaluated using the National Cancer Institute (NCI) Common Terminology Criteria for Adverse Events (CTCAE) Version 5.0 (published 27 Nov 2017) ([NCI, 2017](#)). Further details are given in the [Protocol Section 8.3](#) and [Protocol Appendix 3](#).

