7.4.2. Adverse Events

The verbatim terms as reported in the CRF by Investigators to identify AEs will be coded using the MedDRA, Version 22.0 or higher and summarized by primary SOC and PT.

Adverse event toxicity will be evaluated using the NCI CTCAE Version 5.0 (published 27 Nov 2017).

Adverse event causality is determined by the Investigator using the following assessment categories: unrelated, or related.

Treatment-emergent AEs are defined as those AEs with onset on or after the first dose of treatment (ie, study drug). Events reported with a partial onset date (eg, month and year are reported but the day is missing) will be considered to be treatment-emergent if it cannot be confirmed that the event onset was prior to the first dose of study drug based on the available date entries.

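### SAP 9.2.1 has no rule for an adverse event dated on the first-dose day without a start time, and its catch-all contradicts its own gloss on that event

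*SAP*

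**What the plan says.** SAP 9.2.1, in the technical specifications for derived variables, gives the main rule: "Treatment-emergent AEs are events with start dates and start times on or after the date and time of the first study drug dose". The rules for incomplete data follow, and their trigger concerns the date: "If the start date of an AE is partially or completely missing" (and the stop date and time do not show a pre-dose event). Most of these branches lead to treatment-emergent status. For example, with the day missing in the dosing year: "the start month is present and is the same or after the month of the first study drug dose, then the AE is treatment-emergent". A completely missing start date also gives a treatment-emergent event. The section ends with a residual class: "All other AEs are considered PTAEs (ie, AEs with partial or complete start dates before first study drug dose".

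SAP 7.4.2 gives the definition used for the analysis: "Treatment-emergent AEs are defined as those AEs with onset on or after the first dose of treatment (ie, study drug". It does not mention clock time. For incomplete dates it begins "Events reported with a partial onset date (eg, month and year are reported but the day is missing" and says that such events "will be considered to be treatment-emergent if it cannot be confirmed that the event onset was prior to the first dose of study drug".

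SAP 5.3.1 describes what is recorded for each event: "information regarding its seriousness, start and stop dates, toxicity, outcome, and causal relationship with the study drug will be provided". Start time is not in that list. Protocol 6.4 does require the date and time of every dose to be recorded.

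**The concern.** The two sections put the burden of proof in different places. SAP 7.4.2 requires pre-dose onset to be shown before an event leaves the treatment-emergent class. The SAP 9.2.1 catch-all sends to the pre-treatment class whatever the earlier sentences have not captured. An event on the first-dose date with no time is not captured.

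Day 1 matters here. Prior exposure to ALXN1840 is an exclusion (Protocol 5.2, criterion 22), and Protocol 4.2 puts the peak of total Mo at about 4.5 to 6 hours after a single dose. A reaction around the first peak would therefore usually carry the Day 1 date. If it has no time and is coded PTAE, it leaves the treatment-emergent tables: overall, related, by grade and leading to withdrawal. For an event that truly began after dosing, this error can only lower the treatment-emergent count.

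**Working it through.** The plan states no figure on this point, so the check is a trace of both rules over 11 onset patterns. Three assumptions apply:

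- No stop date shows that the event ended before dosing.
- A date strictly before or after the first-dose date settles the comparison whatever the time.
- The SAP 7.4.2 default is applied to any incomplete onset, including a missing time. This extends its wording, which speaks of a partial date.

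| Onset information | SAP 9.2.1 | SAP 7.4.2 |
|---|---|---|
| First-dose date, time after dose | TEAE | TEAE |
| First-dose date, time before dose | PTAE | PTAE |
| **First-dose date, no time** | **PTAE by the catch-all, but its gloss is false** | **TEAE** |
| Later date, no time | TEAE | TEAE |
| Earlier date, no time | PTAE | PTAE |
| Day missing, month of first dose | TEAE | TEAE |
| Day and month missing, year of first dose | TEAE | TEAE |
| Day missing, earlier month of that year | PTAE | PTAE |
| Earlier year only | PTAE | PTAE |
| Date completely missing | TEAE | TEAE |
| Day and month present, year missing | PTAE by the catch-all | TEAE |

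The sections agree on 9 of 11 patterns. The missing-year pattern is improbable in a resident unit and carries little weight. The pattern that matters is the third, which SAP 9.2.1 handles as follows:

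1. The main sentence compares a start date and time with the dose date and time. Without a start time the comparison cannot be made.
2. The fallback branches require an incomplete date. This date is complete, so none applies.
3. The catch-all takes every other event and makes it a PTAE.
4. The gloss in the same sentence describes PTAEs as events dated before the first dose. This event is dated on the day of that dose, so the gloss does not fit.

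The operative words and the gloss therefore give different answers. The ordering is also odd: an event with no date at all is treatment-emergent, and so is one known only to the dosing month, while one known to have begun on the dosing day is not reliably so.

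**Size.** SAP 7.4.2.1 takes the percentage as n/N × 100, with participants as the unit and the Safety Set as N. SAP 6.5 defines that set as everyone dosed, and SAP 9.1 plans about 17. One participant moved out of the numerator changes the incidence by 1/17 × 100 = 5.9 percentage points. For overall incidence this requires that the participant has no other treatment-emergent event. For a single table row it requires no other such event in that row.

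**The case against.** The strongest reply is that the text does not settle on PTAE. The gloss excludes a Day 1 date, SAP 9.2.1 opens by pointing to SAP 7.4.2 for the analysis of adverse events, and the definition there asks for no clock time. A sensible programmer might reach the right answer. That stands to the extent that the outcome is undetermined, not certainly wrong. It does not supply the missing rule, and SAP 9.2.1 is the specification from which the flag would be derived.

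Second, the default in SAP 7.4.2 is written for a partial date, with a missing day as its example. Strictly, the conflict is with its principle and not with an explicit rule on times. This is correct.

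Third, the omission of times from SAP 5.3.1 does not show that they are not collected. That section is a summary, SAP 9.2.1 itself refers to start times and stop times, and participants are resident on Day 1. The CRF is not available, so no frequency can be given.

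Fourth, the events would not disappear. SAP 7.4.2.1 and 7.4.2.2 require PTAEs to be summarized and listed, and the listings of serious events, deaths and withdrawals are not described as limited to treatment-emergent events. This also stands.

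A reader might infer more than the documents support:

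- *That SAP 9.2.1 ignores incomplete data or broadly conflicts with SAP 7.4.2.* It does not; its missing-date branches mostly agree with that section.
- *That dosing decisions would be affected, because Protocol 6.6.1 defines an adverse reaction as a related treatment-emergent event.* Those rules are applied during conduct by the investigator, the sponsor and the Safety Review Committee, and the committee reviews all adverse events from the first group (Protocol 9.7). A flag derived for analysis does not govern them.
- *That several participants would be affected, or that the 13 completers are the denominator.* The documents give no count, and the denominator is the Safety Set.

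**Conclusion.** The point holds as a gap and an internal contradiction in SAP 9.2.1, limited to an event dated on the first-dose day with no start time. Read literally, the catch-all makes that event pre-treatment; read by its gloss, it does not. The literal reading runs against SAP 7.4.2.

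The effect is 5.9 percentage points of overall treatment-emergent incidence for each participant whose only such event is of this kind. This assumes 17 treated participants, literal programming, and an event that truly began after dosing. The number of participants affected is unknown and may be zero if the CRF captures start times. Safety analyses are descriptive, so no test is affected. The consequence is a relabelling of possible first-dose events, which remain visible among the PTAEs. It is still worth correcting before programming, because the error would understate treatment-emergent events and the remedy is very small.

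**What to change.** Add to SAP 9.2.1: *If the start date equals the date of first dose and the start time is missing, the AE is treatment-emergent unless the available entries confirm onset before first dose.*

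Replace the catch-all with: *An AE is a PTAE only if its available date and time entries confirm onset before first dose; otherwise it is treatment-emergent.* This also settles the missing-year case and brings SAP 9.2.1 into line with the principle in SAP 7.4.2.

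Confirm whether the CRF collects the start time of adverse events, at least on Day 1.

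The cost is two sentences in the SAP and a small change to the derivation. The drawback is that an untimed Day 1 event that in truth preceded the dose will occasionally be counted as treatment-emergent, which is the conservative direction for safety.
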